7.5 Required Observations Following Completion of Protocol Therapy

When a patient discontinues the study, a Final Visit will be conducted. Following discontinuation of the study drug, the patient will be treated in accordance with the investigator's best clinical judgment. If a patient discontinues from the study due to an adverse event considered possibly or probably related to study drug, a Follow-up Visit must be conducted no later than 30 days after the last dose of anti-cancer therapy administered as part of this protocol. Safety assessments will be conducted at least every 30 days, until all toxicities resolve, return to baseline or become clinically satisfactory, stable, or are considered irreversible.

Upon completing protocol therapy or exiting the study, all patients will be followed for life or until otherwise notified by the study committee that the study is closed. Sites should submit follow-up a minimum of every 6 months. Events such as patient death, relapse or development of toxicity related to this therapy should be reported right away. The purpose is to assess safety, remission status, administration of alternative therapies, and survival.

The following data will be collected:

- 1) Disease status information
- 2) Anti-cancer therapy received after exiting the protocol
- 3) All adverse events thought to be related to this study's treatment
- 4) Date and cause of death

8.0 CRITERIA FOR REMOVAL FROM PROTOCOL THERAPY, OFF STUDY CRITERIA AND STUDY TERMINATION

8.1 Criteria for Removal from Protocol Therapy

- a. Completion of protocol therapy
- b. Progressive disease
- c. Patient/parent withdrawal or refusal after beginning protocol therapy
- d. Patient/parent withdrawal or refusal before beginning protocol therapy
- e. Patient off treatment for other complicating disease
- f. Non-compliance with protocol regimen and procedures
- g. Unacceptable toxicity
- h. Investigator determination
- i. Female patient becomes pregnant or begins breast-feeding

8.2 Off Study Criteria

- a. Death
- b. Patient Lost to follow-up
- c. Patient withdraws consent, refuses follow-up

8.3 Termination of the Study by TACL

The TACL Consortium may terminate this study prematurely, either in its entirety or at an investigative site, for reasonable cause provided that written notice is submitted in advance of the intended termination. Advance notice is not required if the study is stopped due to safety concerns.

9.0 STATISTICAL CONSIDERATIONS

The Phase I sample size for each dose level and each of the three cohorts is 6 evaluable patients for the primary endpoint, consistent with the sample size typically sufficient to demonstrate regimen tolerability in Phase I trials. The maximum sample size in any cohort at a particular dose level is 12 evaluable patients, including 6 evaluable patients for expansion.

As of Protocol Amendment #3, Cohort A will enroll at DL1 only. Cohort B will utilize DL1 and Cohort C will continue treatment at DL2. Dose escalation for Cohort B and de-escalation for Cohort C may still occur per study design.

The focus of the study design and statistical analysis is to determine whether Marqibo® can be substituted for standard vincristine and successfully administered to patients with relapsed ALL in three different treatment cohorts: (A) treatment with the UK ALL R3 regimen; (B) treatment with UK ALL R3 regimen without mitoxantrone, and (C) treatment with ALL maintenance therapy. Secondary objectives include estimating rates of serious toxicities and therapy delays in each of these cohorts. Achievement of response and achievement of an MRD undetectable status will only be evaluated in Cohorts A and B, as Cohort C is not being used to eradicate disease, rather is only intended for the purposes of disease stabilization.

9.1 Endpoints

9.1.1 Primary Endpoint

Cohort A

The primary endpoint in Cohort A is whether a patient is successfully treated with UK ALL R3/Marqibo® at nearly full dose without inordinate delays in the resolution of hematologic and non-hematologic toxicity that preclude timely continuation with subsequent treatment.

Specifically, a patient will be considered successfully treated if:

- a. The patient has received 16 of 20 prescribed doses of Dexamethasone, 2 of 2 prescribed doses of Mitoxantrone, 3 of 4 prescribed doses of Marqibo®, and 1 of 2 doses of pegaspargase.
- b. The patient has not experienced a dose limiting toxicity (DLT) as defined in section 4.2.

A patient will be considered NOT successfully treated if (s)he has experienced a dose limiting toxicity (DLT) as defined in section 4.2, or has received fewer than the minimum numbers of prescribed doses as described in (a) above for reasons not unequivocally unrelated to treatment toxicity (see section 9.3.1)

Cohort B

The primary endpoint in Cohort B is whether a patient is successfully treated with UK ALL R3/Marqibo® without mitoxantrone at nearly full dose without inordinate delays in the resolution of hematologic and non-hematologic toxicity that preclude timely continuation with subsequent treatment.

Specifically, a patient will be considered successfully treated if:

- a. The patient has received 16 of 20 prescribed doses of Dexamethasone, 3 of 4 prescribed doses of Marqibo® and 1 of 2 doses of pegaspargase.
- b. The patient has not experienced a dose limiting toxicity (DLT) as defined in section 4.2

A patient will be considered NOT successfully treated if (s)he has experienced a dose limiting toxicity (DLT) as defined in section 4.2, or has received fewer than the minimum numbers of prescribed doses as described in (a) above for reasons not unequivocally unrelated to treatment toxicity (see section 9.3.1)

Cohort C

The primary endpoint in Cohort C is whether a patient is successfully treated with one cycle (14 days) of the modified maintenance treatment at nearly full dose without inordinate delays in the resolution of non-hematologic toxicity that preclude timely continuation with subsequent treatment.

Specifically, a patient will be considered successfully treated if during the first course of modified maintenance treatment:

- a. The patient has received 8 of 10 prescribed doses of dexamethasone, and 1 of 1 prescribed doses of Marqibo®, 1 or 2 prescribed doses of Methotrexate, and at least 50% of doses of mercaptopurine
- b. The patient has not experienced a dose limiting toxicity (DLT) as defined in section 4.2

A patient will be considered NOT successfully treated if (s)he has experienced a dose limiting toxicity (DLT) as defined in section 4.2, or has received fewer than the minimum numbers of prescribed doses as described in (a) above for reasons not unequivocally unrelated to treatment toxicity (see section 9.3.1)

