3.4 Exclusion Eligibility Criteria

3.4.1 Active CNS disease (CNS 3) is exclusionary. Patients with CNS 1 or CNS 2 disease may be enrolled, which is inclusive of patients with a recent history of CNS3 disease which is now resolved to CNS1 or CNS2

3.4.2 Patients will be excluded if they have any isolated extramedullary disease, including isolated testicular or isolated CNS disease.

3.4.3 Patients will be excluded if they have previously received Marqibo®.

- 3.4.4** Patients will be excluded if they have a known allergy to any of the drugs used in the study, with the exception that patients with an allergy to pegaspargase who can receive Erwinia asparaginase are eligible. Patients unable to receive any formulation of asparaginase may only enroll on cohort C
- 3.4.5** Patients will be excluded if they have active, uncontrolled systemic fungal, bacterial, viral or other infection despite appropriate antibiotics or other treatment.
- 3.4.6** Patients who require azole antifungal agents will be excluded. Azoles must be discontinued at least one week prior to the start of Marqibo®.
- 3.4.7** Patients will be excluded if there is a plan to administer non-protocol chemotherapy, radiation therapy, another investigational agent or immunotherapy during the study period.
- 3.4.8** Patients with pre-existing, persistent grade 2 or greater sensory or motor neuropathy from any cause will be excluded. (Patients on chronic stable doses of gabapentin or similar agents for history of neuropathy may be included if there are no active neuropathic symptoms)
- 3.4.9** Patients will be excluded if they have significant concurrent disease, illness, psychiatric disorder or social issue that would compromise patient safety or adherence with the protocol treatment or procedures or interfere with consent, study participation, follow up, or interpretation of study results.
- a. Patients with Down syndrome will not be eligible for enrollment on Cohort A
- 3.4.10** Patients with a known history human immunodeficiency virus (HIV) will be excluded due to the increased risk of complications such as severe infection and unknown interaction of Marqibo® with antiretroviral drugs.
- 3.4.11** Active hepatitis B or C infection as defined by seropositive for hepatitis B (hepatitis B surface antigen (HBsAg)) or hepatitis C and elevated liver transaminases (defined as above the ULN per the institution normal ranges).

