- If available and FDA approved, asparaginase Erwinia chrysanthemi (Erwinaze®), asparaginase Erwinia chrysanthemi (recombinant)-rywn (Rylaze®) or crisantapase (Erwinase®) may be substituted for pegaspargase in patients with systemic allergic reaction.
- o Asparaginase Erwinia chrysanthemi (Erwinaze®) or Cristantapase (Erwinase®): May be dosed per package insert guidelines as 25,000 IU/m²/dose IM or IV over 1-2 hours. Give 6 doses of asparaginase Erwinia chrysanthemi (Erwinaze®) or Cristantapase (Erwinase®) over 2 weeks on a schedule of every other day (for example, q 48 hours, or M/W/F dosing) for each dose of planned pegaspargase.

- o Erwinia chrysanthemi (recombinant)-rywn (Rylaze®): Refer to current FDA product information for dosing at the time of product administration.
- o For any Erwinia formulation, **each individual dose not to exceed pegaspargase equivalent dosing of 3,750 IU (i.e., cap individual dose at 37,500 IU Erwinia)**. Route of administration, dose schedule and total doses administered should be documented, as this could contribute to variability in PK data for Marqibo®.
- Dose may be administered by IM or IV per product information guidelines (Please document route of administration).
- Premedications may be given per institutional standard.

Intrathecal methotrexate

- Given intrathecally to all patients the dose defined by age below on days 1 and 8 (+ 2 days). *Note:* The “Day 1” intrathecal chemotherapy dose may be given during eligibility screening evaluation within two weeks prior to Day 1 chemotherapy, and does not need to be repeated on Day 1. Alternatively, per standard of care, ARA-C and hydrocortisone may be substituted if methotrexate is contraindicated.
- IT methotrexate may also be given at day 29 (+/- 2 days) during disease assessment
- Timing of IT methotrexate is flexible in regards to timing of Marqibo®. However, these agents should not be given simultaneously in order to reduce the risk of administration route error.

Age (years)	Methotrexate (mg)
1-1.99	8 mg
2-2.99	10 mg
3-8.99	12 mg
≥ 9	15 mg

Cohort B: ALL R3/Marqibo without anthracycline

	Day 1	Day 2	Day 3	Day 4	Day 5	Day 8	Day 15	Day 16	Day 17	Day 18	Day 19	Day 22	Day 29	Response Evaluator	
Marqibo®	●					●	●						●		
Dexamethasone	●	●	●	●	●		●	●	●	●	●				
Pegaspargase[#]			●						●						
IT Methotrexate	●					●									

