9.3 Patient Evaluability

9.3.1 Definition of a patient evaluable for the primary endpoint

A patient will be considered evaluable for the treatment success endpoint (section 9.1.1) if (s)he receives any portion of treatment, except if treatment or follow-up is terminated for reasons unequivocally unrelated to treatment toxicity (e.g., if a drug is omitted from the regimen for reasons aside from toxicity, or treatment is terminated because of problems unequivocally related to disease progression). Patient who are not evaluable for the primary endpoint will be replaced.

9.3.2 Definition of a patient evaluable for toxicity:

Any patient who receives at least one dose of any drug on study will be considered evaluable for toxicity.

9.3.3 Definition of a patient evaluable for response:

A patient will be considered evaluable for response if the patient receives all or part of protocol therapy and the patient is under follow-up for a sufficient period to evaluate the disease at the end of protocol therapy or to meet the definition of progressive disease. A patient who dies as a result of toxicity after receiving all or part of protocol therapy, or who is removed from therapy for problems possibly related to disease progression, will be considered a non-responder.

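### In Cohorts A and B the success criterion counts only pegaspargase doses, so an eligible patient allergic at entry and treated with Erwinia can never be a success

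*Combined protocol and SAP*

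**What the plan says.** **Endpoint.** Criterion (a) of 9.1.1 sets dose minimums for success. In Cohort A these include "3 of 4 prescribed doses of Marqibo®, and 1 of 2 doses of pegaspargase"; Cohort B has the same asparaginase minimum. Neither 9.1.1 nor 9.3.1 mentions Erwinia. A patient below a minimum is not successfully treated if the shortfall arose "for reasons not unequivocally unrelated to treatment toxicity".

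**Eligibility.** Section 3.4.4 states that "patients with an allergy to pegaspargase who can receive Erwinia asparaginase are eligible". It adds: "Patients unable to receive any formulation of asparaginase may only enroll on cohort C". Patients who can take Erwinia may therefore enter Cohort A or B.

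**Treatment.** Under section 4.1 the Erwinia products "may be substituted for pegaspargase in patients with systemic allergic reaction". For two of them there is an explicit correspondence: "Give 6 doses of asparaginase Erwinia chrysanthemi (Erwinaze®) or Cristantapase (Erwinase®) over 2 weeks", and this applies "for each dose of planned pegaspargase". For the recombinant product, 4.1 refers to the product information and gives no such correspondence.

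**Evaluability.** Section 9.3.1 excepts patients whose treatment or follow-up ends for reasons unequivocally unrelated to treatment toxicity. One of its examples is "if a drug is omitted from the regimen for reasons aside from toxicity". Non-evaluable patients are replaced.

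**DLT.** Section 4.2.1.1 defines a non-hematological DLT partly by whether a Grade 3 or greater attributable toxicity stops the patient from receiving the dose numbers that Section 9.0 requires. The pegaspargase-only count is therefore part of the DLT definition as well.

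**The concern.** The treatment section treats an Erwinia course as the stand-in for a planned pegaspargase dose; the endpoint does not. A patient can be enrolled as the protocol allows, complete every asparaginase treatment the protocol prescribes, have no DLT, and still miss criterion (a). No literal reading makes that patient a success.

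The endpoint drives decisions on very few patients. Section 9.2 considers escalation when no more than 1 of the first 6 evaluable patients is treated unsuccessfully, and de-escalation when more than 1 is. It also gives a limit of 2 in 6 for re-escalating Cohort B, and it suspends the study for review when more than one third of evaluable patients fail. With such thresholds the classification of one patient matters. If the choice between failure and replacement is left open, it may be made case by case after the outcome is known.

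**Working it through.** **1. The plan's own monitoring rule.** Section 9.2 uses a Beta(1,4) prior and flags when the posterior probability that the failure rate exceeds 0.10 is above 0.80. It states the boundary as 2 or more failures in the first 5 expansion patients, then 3 or more in the first 6. With x failures in n patients the posterior is Beta(1+x, 4+n−x). The stated boundary reproduces when the expansion data are pooled with 6 Phase I patients who had no failures:

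| Failures / patients | P(rate > 0.10) |
|---|---|
| 1/11 | 0.549 |
| 2/11 | 0.816 |
| 2/12 | 0.789 |
| 3/12 | 0.932 |

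Reclassifying a single patient moves the result across the 0.80 line, from 0.549 to 0.816 at n = 11 and from 0.789 to 0.932 at n = 12.

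**2. Classifying the patient who is allergic at entry.** Pegaspargase doses received: 0 of 2. Minimum: 1 of 2. Criterion (a) is not met. Two branches remain.
- *Failure.* The omission is not unequivocally unrelated to treatment toxicity, so 9.1.1 applies.
- *Replacement.* The drug was omitted for a reason other than toxicity, so 9.3.1 applies. A patient with a DLT is still, under 9.1.1, not successfully treated.

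The text does not choose. An allergy from earlier treatment is arguably a toxicity, but not of this study's treatment. The main clause of 9.3.1 speaks of treatment or follow-up being terminated, while its example speaks of a drug being omitted.

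**3. Size on the failure branch.** Assume a true failure rate of 10% in the other patients. Let k of the 6 be Erwinia patients counted as failures.

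- k = 0: P(more than 1 failure) = 1 − 0.9^6 − 6 × 0.1 × 0.9^5 = 1 − 0.531 − 0.354 = 0.114.
- k = 1: at least 1 failure is needed among the other 5, so 1 − 0.9^5 = 0.410.
- k = 2: 1.00.

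On the limit of 2 in 6, P(3 or more failures) is 0.016, 0.081 and 0.344 for k = 0, 1 and 2.

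The share q of such patients is not in the documents. Over an assumed range, the apparent failure rate is q + (1−q) × 0.10:

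| q | Apparent rate | P(more than 1 in 6) |
|---|---|---|
| 0 | 10% | 0.114 |
| 5% | 14.5% | 0.212 |
| 10% | 19% | 0.320 |
| 20% | 28% | 0.536 |
| 30% | 37% | 0.717 |

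**4. Size on the replacement branch.** Assume Erwinia patients also fail at 10%, and that those with a DLT are counted while the rest are replaced. All failures then enter (0.10), but only non-Erwinia successes do (0.90 × (1−q)). The apparent rate is 0.10 / [0.10 + 0.90 × (1−q)]:

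| q | Apparent rate | P(more than 1 in 6) |
|---|---|---|
| 5% | 0.10/0.955 = 10.5% | 0.124 |
| 10% | 0.10/0.910 = 11.0% | 0.134 |
| 20% | 0.10/0.820 = 12.2% | 0.160 |
| 30% | 0.10/0.730 = 13.7% | 0.193 |

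**5. Who is outside the problem.** A patient who receives the day 3 pegaspargase dose, reacts and switches to Erwinia has 1 of 2 doses. The minimum is met and success remains possible.

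**The case against.** The authors probably meant an Erwinia course to count. The 6-for-1 correspondence in 4.1 points that way, and a committee would see that a patient on full Erwinia without a DLT had not failed for toxicity. Section 9.2 says the design is not prescriptive: crossing a threshold leads to review, and escalation and de-escalation are considered, not automatic. Cohort A now enrolls at dose level 1 only, so re-escalation remains open only in Cohort B. All of this stands and limits the harm. It does not supply the missing rule, because Section 9 still classifies the patient by pegaspargase alone.

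Four stronger readings are tempting, and the documents do not support them.
- *Anyone who reacts on study and switches is a failure.* No: the day 3 dose already meets the minimum. A dose stopped partway is at most ambiguous, since the text does not say how partial doses count.
- *The toxicity table in 6.5.2 gives the share affected, 5 to 20 per 100.* No: that row covers local or systemic reactions within 1 to 2 days of receiving the drug in patients without earlier hypersensitivity. It is not the share allergic at entry.
- *Every affected patient is counted as a failure, moving the rate by 1/6, or about 17 points.* That holds only on the failure branch. On the replacement branch a patient without a DLT leaves the denominator, and one with a DLT is a true failure; the bias comes only from dropping the successes.
- *Requiring the complete Erwinia course would repair it.* That is undefined for the recombinant product. It would also be stricter than the other minimums: 5 of 6 doses in each course (10 of 12) would fall short, while 16 of 20 dexamethasone doses and 3 of 4 Marqibo doses suffice.

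**Conclusion.** The point holds for patients in Cohorts A and B who are allergic to pegaspargase at entry and receive only Erwinia. They are eligible and treated as the protocol allows, yet cannot be successes. This is a stated rule that misclassifies patients, not merely missing detail.

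The size depends on the branch taken and on a share that the documents do not give. One such patient counted as a failure among 6 raises the chance of more than 1 failure from 0.11 to 0.41, at an assumed true rate of 10%. Under replacement with DLTs still counted, the effect is modest: 10.5% to 13.7% against 10%, for assumed shares of 5% to 30%, with equal failure risk on Erwinia. Both act upward on the apparent failure rate. It should be corrected, but it does not show that any past dose decision was wrong.

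**What to change.** 1. In 9.1.1, for Cohorts A and B, replace the pegaspargase minimum with: *1 of 2 planned asparaginase doses, where an Erwinia substitution given under section 4.1 in place of a planned pegaspargase dose counts as that dose*.
2. State the minimum share of the substituted Erwinia doses needed for the substitution to count, in keeping with the endpoint's intent of near-complete dosing. Cover the recombinant product explicitly, since 4.1 gives no dose correspondence for it.
3. State in 9.3.1 that a pre-existing pegaspargase allergy managed with Erwinia does not make a patient non-evaluable.

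Section 4.2.1.1 then takes over the corrected count through its reference to Section 9.0. No treatment rule changes. The cost is a few sentences; 4.1 already calls for the route, schedule and number of Erwinia doses to be documented.

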9.1.2 Exploratory Endpoints

- a. Occurrence of toxicity, as graded using the NCI's Common Terminology Criteria for Adverse Events (CTCAE 4.03).
- b. (Cohorts A and B) Achievement of CR or CRi during the course of therapy.
- c. (Cohorts A and B) In those who achieve CR or CRi, achievement of MRD negative status (i.e., $<10^{-4}$ blasts by flow cytometry in a central lab).
- d. Pharmacokinetic assessment of Marqibo®

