1.2 Exploratory Objectives

- 1.2.1 To describe the constellation of toxicities experienced by patients treatment with each of these three regimens.
- 1.2.2 To describe the number of patients who achieve a complete remission (CR), including CR + CR with incomplete blood count recovery (CRi) rate for patients with acute lymphoblastic leukemia (ALL) and first to third relapse who are treated in cohorts A and B.
- 1.2.3 To describe the number of patients with CR at end of induction who become minimal residual disease (MRD) negative by flow cytometry (i.e., $< 10^{-4}$ blasts in a central lab) in cohorts A and B.
- 1.2.4 To assess the pharmacokinetics of Marqibo® when used in combination with the UK ALL R3 induction chemotherapy regimen, in UK ALL R3 induction chemotherapy without mitoxantrone, and in ALL maintenance therapy.

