3.3.2 Diagnosis

Cohort A: Patients must have a diagnosis of acute lymphoblastic leukemia (ALL, T or B cell) or mixed phenotypic acute leukemia with $\geq 5\%$ blasts in the bone

marrow (M2 or M3 by aspirate or flow cytometry), with or without extramedullary disease) or a diagnosis of lymphoblastic lymphoma.

Cohorts B & C: Patients must have a diagnosis of acute lymphoblastic leukemia (ALL, T or B cell), lymphoblastic lymphoma, or mixed phenotypic acute leukemia with any level of detectable disease (minimal residual disease level acceptable) with or without extramedullary disease

3.3.3 Performance Level Karnofsky > 50% for patients > 16 years of age and Lansky > 50% for patients ≤ 16 years of age. (Appendix 1)

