7.4.1 Bone Marrow MRD

Samples requested:	
Bone Marrow Sample for MRD
 
 • Pre-treatment: optional* • Day 29 (+/- 2 days) 
Sample should also be submitted if the bone marrow procedure is repeated after day 29 to document marrow and count recovery. * Repeat bone marrow for this purpose is not required. For patients with circulating blasts, 10 mL of peripheral blood in a heparinized tube may be submitted. For all patients, prior flow cytometry report should be submitted.
 
*Bone Marrow MRDs are performed as part of standard of care, however, the information from them will be used for research purposes.
 
Not required for cohort C.

Bone marrow Collection procedure:	
 • Collect minimum of 2 mL of marrow into a syringe and place marrow into a large purple EDTA tube that are commonly used in all hospitals. Mix well. • Use multiple syringes and tubes as needed. Reposition marrow aspirate needle as least once during procedure to ensure the maximum quality of marrow
Specimen Labeling:	Please refer to the TACL MRD Lab Manual for instructions regarding specimen labeling.
Specimen Packaging and Shipping:	Please refer to the TACL MRD Lab Manual for instructions regarding specimen packaging and shipping.

*Results from MRD assessments must be forwarded to TACL Operations at [contact]

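### A Cohort B patient who enters with MRD below 10⁻⁴ and does not change counts as MRD negative, because the MRD endpoint has no baseline condition

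*Combined protocol and SAP*

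**What the plan says.** - **Entry.** Section 3.3.2 accepts Cohort B (and C) patients with "any level of detectable disease (minimal residual disease level acceptable". It names no assay, sensitivity or numeric floor. Cohort A patients with leukemia need at least 5% blasts in "marrow (M2 or M3 by aspirate or flow cytometry), with or without extramedullary disease".
- **Objective.** Section 1.2.3 describes, for Cohorts A and B, the number of patients in CR "who become minimal residual disease (MRD) negative by flow cytometry".
- **Endpoint.** Section 9.1.2(c) is "In those who achieve CR or CRi, achievement of MRD negative status", with negative set at below 10⁻⁴ in a central laboratory.
- **Sampling.** Section 7.4.1 schedules a marrow MRD sample at day 29. The earlier one is "Pre-treatment: optional". It adds: "For all patients, prior flow cytometry report should be submitted". It gives no date window, required sensitivity or use in the analysis for that report.
- **CR/CRi.** Sections 10.1 and 10.2 require an M1 marrow (under 5% blasts) with no circulating blasts or extramedullary disease. CR also requires count recovery. Neither requires the patient to start from M2 or M3.
- **Analysis.** Section 9.3.3 sets no baseline condition for response evaluability. Section 9.4.3 reports MRD-negative rates by cohort and overall, without stratifying by baseline.

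**The concern.** The objective is worded as a conversion: the patient is positive, then becomes negative. The endpoint tests only the second half. In Cohort A the gap hardly matters, because patients with leukemia start at 5% blasts or more, far above 10⁻⁴. In Cohort B the entry level may lie at or below the response limit, so the endpoint can be met with no change in disease.

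The CR/CRi condition does not screen these patients out. A patient with MRD-level disease only and no extramedullary disease already has an M1 marrow.

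At stake are the Cohort B MRD-negative rate and the overall rate that pools it with Cohort A. Section 2.4 hypothesizes better MRD negativity than with historical regimens. A rate that includes patients who were negative at entry by the plan's own threshold cannot inform that question.

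**Working it through.** The plan gives no target, power or expected rate for MRD, so there is no figure to reproduce. The check is in three parts.

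**1. Following the rules for one patient.** A Cohort B patient enters at 5 × 10⁻⁵ on a local assay, with no extramedullary disease.
- Section 3.3.2: disease is detectable, so the patient is eligible.
- Section 10.2: unchanged at day 29 with an M1 marrow, so CR or CRi depending on counts.
- Section 9.1.2(c): a central reading below 10⁻⁴ is MRD negative.
- Sections 9.3.3 and 9.4.3: nothing removes or separates the patient.

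**2. Effect on the reported rate.** Let n be the number of CR/CRi patients, k the number who enter and stay below 10⁻⁴, and c the true conversion rate in the rest.

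Apparent rate = (k + (n − k)c) / n, and its excess over c is k(1 − c)/n.

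Inputs: n = 6 and 12, from the 6 to 12 evaluable patients for Cohort B in Section 9.2, taking all as CR/CRi (fewer would make each patient weigh more). c = 0 is the no-effect case. c = 60% is an illustration from Section 2.3, where 40% of the mitoxantrone arm was MRD positive after Block 1 (1 − 0.40). k is assumed; the documents do not give it.

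| n | k | Rate if c = 0 | Rate if c = 60% |
|---|---|---|---|
| 6 | 1 | 1/6 = 16.7% | (1 + 5 × 0.6)/6 = 66.7% |
| 6 | 2 | 2/6 = 33.3% | (2 + 4 × 0.6)/6 = 73.3% |
| 12 | 1 | 1/12 = 8.3% | (1 + 11 × 0.6)/12 = 63.3% |
| 12 | 2 | 2/12 = 16.7% | (2 + 10 × 0.6)/12 = 66.7% |

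**3. Patients near the threshold.** For an unchanged true level m, the chance of a day 29 reading below 10⁻⁴ is Φ((−4 − log₁₀ m)/SD) under log-normal error. Under counting error it is a Poisson probability. Assumed: SD 0.2 to 0.5 log₁₀, or 200,000 to 1,000,000 events; the plan gives neither.

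| True level | Log-normal | Poisson |
|---|---|---|
| 5 × 10⁻⁵ | 73–93% | 99.7–100% |
| 10⁻⁴ | 50% | 47–49% |
| 1.5 × 10⁻⁴ | 19–36% | 0–2% |
| 2 × 10⁻⁴ | 7–27% | about 0% |
| 10⁻³ | 0–2% | about 0% |

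Below the threshold, a negative reading is likely to near certain. At it, the result is a coin toss. Just above it, the answer depends on the error model. One log above, it is rare.

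A simulation across MRD-level entrants gives the same picture. Assumptions: log-uniform true level up to 5%; independent entry and day 29 errors with SD 0.3 to 0.5 log₁₀; entry reading at or above the assay limit; no change in disease; true levels either starting at the assay limit or extending below it. The share reading below 10⁻⁴ at day 29 is 3–11% for an entry-assay limit of 10⁻⁴, 25–29% for 10⁻⁵ and 42–44% for 10⁻⁶. These are shares of MRD-level entrants, not of Cohort B.

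**The case against.** Much of the case on the other side stands, and it limits the point without removing it.

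- **Exploratory and imprecise.** The aim is description, Section 9.4.3 concedes imprecision, and no dose, stopping or sample-size rule uses MRD. All true. But imprecision does not cancel an error that can only push the rate upward.
- **Nested in CR/CRi.** If patients who are M1 at entry were not counted as achieving CR/CRi, nearly all of these cases would leave 9.1.2(c) as well. That is right, so the two rules should be settled together. If M1 entrants are only reported as a stratum, the MRD gap remains.
- **Baseline data exist.** The prior flow report is requested for every patient, and a marrow evaluation is scheduled before enrollment (Section 7.1). It would be wrong to infer that nothing shows the entry level. The report is not central or standardized, and the endpoint does not use it.
- **Not always a single sample.** Section 7.4.1 asks for another if the marrow is repeated after day 29. This does not supply a baseline.
- **No change is an assumption.** Relapsed disease may grow over four weeks, which lowers the no-effect figures.

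A reader might also infer more than the documents support. No comparison of Cohort A with Cohort B is planned, so there is no planned contrast to call biased. MRD is not the only disease measure that can move in these patients: progression, CNS status, extramedullary disease, and CR versus CRi can all change. Nor can the cohort rate be said to shift by at least 5 points in every case. With a 10⁻⁴ entry limit and 11% of MRD-level entrants crossing, such entrants would have to make up 5/11 = 45% of the cohort. With 3% crossing, even a cohort made up entirely of them would not reach it. The 25–44% figures need entry assays that the documents never mention.

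**Conclusion.** The point holds as a defect in the endpoint definition. Applied as written, Sections 3.3.2 and 9.1.2(c) count an unchanged patient below 10⁻⁴ as a conversion, and no other section prevents it. Each such patient adds (1 − c)/n to the Cohort B rate. That is 16.7 points for n = 6 and 8.3 for n = 12 with no conversion elsewhere, or 6.7 and 3.3 points if 60% of the others convert. The overall rate moves by less, in proportion to its larger denominator.

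The total effect is unknown, because the documents do not give the number of such entrants, their entry levels or the assay error. For patients at or just above 10⁻⁴, crossing without effect is a matter of chance and cannot be presumed. The consequence is confined to interpretation of an exploratory rate. The correction is worth making because it is cheap and the direction of the error is known.

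**What to change.** 1. In Sections 9.1.2(c) and 9.4.3, compute the MRD-negative (conversion) rate only in CR/CRi patients with documented pre-treatment MRD of at least 10⁻⁴, the plan's own threshold.
2. List CR/CRi patients with baseline below 10⁻⁴ or unknown separately, with their baseline and day 29 values.
3. Within the rate, show patients entering between 10⁻⁴ and 10⁻³ as a subgroup. Under the simulation assumptions, 3–11% of MRD-level entrants reading at or above 10⁻⁴ would still cross by variation alone, mostly in this band. A 10⁻³ floor would remove most of that, but it has no basis in the documents and would drop patients whom the plan itself calls MRD positive.
4. In Section 7.4.1, take the Cohort B baseline from a central aliquot of the entry marrow where available. Otherwise use the prior flow report, recording its date, assay and sensitivity.
5. Settle this together with any CR/CRi rule for patients who are M1 at entry.

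The cost is analysis wording, shipment of an aliquot from a marrow already taken, and a smaller denominator for a descriptive rate. No extra procedure is needed, and eligibility and treatment do not change.
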